Potential participants will be recruited via flyers and staff meetings. Interested individuals will be invited to call the clinical research coordinator to discuss eligibility criteria. If they meet eligibility criteria, the research coordinator will discuss the informed consent form. For eligible and interested individuals, consent will be emailed via REDCap (Research Electronic Data Capture).

6) Number of Participants*

The overall study aims to enroll one cohort up to 25 participants in total.

7) Study-Wide Recruitment Methods*

This is not a multicenter study. All study-related recruitment will be at the Sylvester Comprehensive Cancer Center. Potential participants will be recruited via flyers and staff meetings. Interested individuals will be invited to contact the study team directly. A study team member will then screen for eligibility and initiate the process of informed consent. For interested and eligible individuals, consent will be obtained and the decision to join the study will be documented. A member of the study team will then perform consent procedures by presenting the individual with a detailed, consent form to be electronically signed following the explanations by the study team member.

8) Procedures Involved*

After eligibility is determined and electronically written consent is obtained, study procedures will continue as follows:

Upon enrollment of our target sample (up to 25 enrollees), all participants will receive an email link to complete an online baseline assessment in REDCap. This will ensure that all participants complete the assessment within the same approximate timeframe.

Light food and beverage will be provided at each educational session. The training sessions will take place in the University of Miami IRB-approved HIPPA-compliant location at the Sylvester Comprehensive Cancer Center. Training sessions with participants may be recorded or filmed for the purposes of missed-session make up (see #11 'Data Storage' bottom paragraph), training quality assurance, and practice materials. Participants will receive up to 16 nursing continuing education credits, one for each hour of the program that they attend. Additionally, as *compensation* for their time and effort, all participants will receive a \$15 gift card after completing the post assessment.

Program

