We will compare changes from baseline to 7-10 weeks in the Perceived Stress Scale between the participants who completed the educational program and participants on the waitlist with a paired t-test. If the two-sided p-value is $\leq .05$, our hypothesis that the program results in reduction of perceived stress will be supported.

Similarly, we will compare differences from baseline to 7-10 weeks in scores on the Self-Efficacy Scale; Maslach Burnout Inventory; the two components of the Philadelphia Mindfulness Scale (Present-Moment Awareness and Acceptance); the Distress Tolerance Scale; and the SF-36.

Power Analysis

Effect sizes for changes in psychological factors following a compassion-based educational intervention in oncology nurses have not been tested. The goal of this trial is to estimate effect sizes for a larger adequately-powered trial. The sample size is similar to other small feasibility studies of educational interventions in healthcare workers. We will conduct hypothesis testing to examine differences in our endpoints from pre- to post-intervention, to aid in planning a future trial.

14) Provisions to Monitor the Data to Ensure the Safety of Participants*

There will be no independent monitoring of the data outside of the study staff and the UM IRB.

To ensure the usability of self-report data, the research coordinator will review all assessment measures to ensure their completeness.

All participant data will be kept in a computer file that is password protected and changed whenever staff changes. Only study staff will have access to these data. A link between ID number and participant's name will be kept in a separate file, also password protected (with a different password), accessible only to the study PI and research coordinator.

We do not plan to employ a Data Safety Monitoring Board because potential risks to participants are minimal.

OUTCOMES MONITORING

Quality Assurance of Collected Data

Data collection will be conducted in the form of assessments completed on-line via e-mail and in some cases via mail. The research coordinator will also review all measures to ensure their completeness, and tracking forms will be developed to ensure that the assessments have occurred.

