21) Confidentiality*

All participants will be assigned a unique study ID number. Identifying information will be stored separately from other study data in a password-protected, encrypted Excel file. All data will be stored on secure servers at the University of Miami. REDCap software will be utilized during the study to maximize data security. Only authorized study personnel will have access to identifying information throughout the course of the study.

22) Local Number of Participants*

The maximum number of participants to be recruited locally is 25.

23) Consent Process*

Oncology nurses who work at the University of Miami Sylvester Comprehensive Cancer Center may receive a flyer that will instruct them to reach out to the research coordinator to discuss eligibility. If they meet eligibility criteria and are interested in participating, informed consent will be presented in the first page of the online survey process, participants will electronically sign and enter their name, and click submit to agree to participate in the study. The consent page on the online survey will be available in English.

24) Process to Document Consent in Writing*

All participants recruited will have to enter their full name to electronically sign the consent before starting the online surveys. The password-protected database to which the data is transferred will be at the University of Miami Miller School of Medicine's secure server, REDCap.

References:

Bruine de Bruin, W., Parker, A.M., & Fischhoff, B. (2007). Individual differences in Adult Decision-Making Competence. *Journal of Personality and Social Psychology*, 92, 938-956.

Chochinov H. (2007) Dignity and the essence of medicine: the A, B, C, and D of dignity conserving care. *BMJ* 334: 184-187.

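### Section 13 reads p ≤ .05 on perceived stress as the program's effect, but one cohort measured once before and once after cannot separate that effect from shared drift or regression to the mean

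*Combined protocol and SAP*

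**What the plan says.** Section 6 (Number of Participants) sets the size and structure: "The overall study aims to enroll one cohort up to 25 participants in total". Section 7 recruits through flyers and staff meetings at one centre. Section 8 (Procedures Involved) fixes when baseline is taken: "Upon enrollment of our target sample (up to 25 enrollees), all participants will receive an email link to complete an online baseline assessment". It gives the reason as keeping all baselines in roughly one period, and it describes eight sessions delivered over 7–10 weeks. Sections 8 and 9 schedule the Perceived Stress Scale twice, at baseline and at 7–10 weeks.

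Section 13 (Data Analysis Plan) compares change in that scale "between the participants who completed the educational program and participants on the waitlist with a paired t-test". The decision rule follows at once. It begins "If the two-sided p-value is" at or below .05 and ends with the conclusion that "our hypothesis that the program results in reduction of perceived stress will be supported". The Power Analysis paragraph in the same section describes a different contrast: "We will conduct hypothesis testing to examine differences in our endpoints from pre- to post-intervention, to aid in planning a future trial". It also says that the trial is meant to estimate effect sizes for a larger one.

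**The concern.** The decision rule draws a causal conclusion, and the only feature of the plan that could support one is the waitlist. If no waitlist exists, every fall in stress between the two measurements is credited to the program.

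Two other sources of change are plausible. The nurses work at one centre and share one training window, so a change in season, staffing or patient load reaches all of them together. They also volunteer, and any who come forward at a stressful time would tend to score lower later without training.

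Two things are at stake: the stated conclusion on the secondary outcome, and the effect size passed to the next trial. An inflated effect would leave that trial too small. A shared rise in stress would do the opposite and hide a benefit.

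**Working it through.** **Step 1. Is there a comparator?** The relevant statements are these.

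- Section 6: a single cohort, at most 25 in total.
- Section 8: every participant gets the baseline link once the target sample is enrolled, and one program of eight sessions is described.
- Section 13, analysis: completers against nurses on a waitlist, by a paired t-test.
- Section 13, Power Analysis: pre- to post-intervention differences.

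In the text available, the waitlist appears only in the one Section 13 sentence. No section describes allocation, a delayed start, or numbers per group. A paired t-test takes two scores from the same person and cannot compare separate groups. The analysis that fits everything else is the single-group change from baseline to 7–10 weeks.

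**Step 2. The plan's own figure.** Section 13 gives no effect size, SD, correlation or power, so there is no calculation to reproduce. The inputs from the documents are n up to 25 and a two-sided level of .05.

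**Step 3. Assumptions, not in the documents.** The program effect is zero. The SD is equal at both times. The baseline-to-post correlation r is 0.6, 0.7 or 0.8. Only significant falls are counted, so the nominal rate is 2.5%.

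**Step 4. Formulas.** With shifts in units of the scale's SD:

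- SD of change = √(2(1 − r)), which is 0.894, 0.775 and 0.632 for the three values of r.
- Standardised change dz = shift ÷ √(2(1 − r)).
- Chance of a significant fall = upper tail of the noncentral t with df = 24, noncentrality dz × √25 and critical value 2.064.
- For regression to the mean, shift = (1 − r) × k, where k is how far the group's baseline lies above the reference mean to which it regresses.

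Example: a shared fall of 0.2 SD at r = 0.7 gives dz = 0.2 ÷ 0.775 = 0.258, and a probability of 23.6%.

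**Step 5. Results at n = 25, no program effect.**

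| Source of the fall | r = 0.6 | r = 0.7 | r = 0.8 |
|---|---|---|---|
| None | 2.5% | 2.5% | 2.5% |
| Shared fall, 0.2 SD | 18.8% | 23.6% | 32.9% |
| Shared fall, 0.3 SD | 36.3% | 46.0% | 62.4% |
| Regression alone, k = 0.25 | 7.7% | 6.7% | 5.7% |
| Regression alone, k = 0.5 | 18.8% | 15.1% | 11.5% |

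**Step 6. Fewer completers.** If 25% drop out, the feasibility limit in Section 13, about 19 of 25 remain (df = 18, critical value 2.101). The ranges become 15–26% for a 0.2 SD fall, 28–50% for 0.3 SD, 5–7% for k = 0.25 and 10–15% for k = 0.5.

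**Step 7. The opposite direction.** A true benefit of 0.4 SD would be detected with 57–86% probability at n = 25. A shared rise of 0.2 SD leaves a net fall of 0.4 − 0.2 = 0.2 SD, detected with 19–33% probability.

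**The case against.** The strongest reply is that Section 13 does name a comparator. A genuine concurrent waitlist would cancel shared calendar change and, if the groups were comparable, most regression to the mean. That is correct, and the point depends on the waitlist not existing. Sections 6 and 8 and the Power Analysis paragraph describe a design without one, and the named test could not use one. The reply therefore shows which sentence to settle first; it does not rescue the causal wording.

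A second reply is that this is a feasibility study: perceived stress is secondary, Objective 2 is to explore, and testing is meant to help plan a later trial. This stands as a limit on severity. It also makes the categorical decision rule harder to justify.

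A third reply is that regression to the mean may be small. Section 5 sets no stress threshold for entry, continuing education credits are another reason to volunteer, and holding baseline until enrollment is complete may let some regression happen beforehand. This stands. The calendar argument is the firmer of the two.

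A reader might also infer from Section 23, where "informed consent will be presented in the first page of the online survey process", that baseline is completed at consent, so that early enrollees have a much longer baseline-to-post interval. The documents do not support that. Sections 23 and 24 set the order of consent and surveys, while Section 8 is the text that fixes baseline timing. No recruitment period is stated from which a longer interval could be computed.

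**Conclusion.** The decision rule is wrong as written. The design provides one score before and one after a shared window, and a significant fall in those scores does not show that the program caused it.

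Under the assumptions in the working, shared falls of 0.2 to 0.3 SD raise the chance of false support from 2.5% to between 19% and 62%. Regression alone gives 6–8% at k = 0.25 and 12–19% at k = 0.5, and its true size is unknown. These figures illustrate sensitivity; they do not predict that stress will drift, or in which direction.

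A reader might go further and suppose that volunteers sit 0.5 SD above their own usual level and return fully to it, which would give 77–97% on the same method. Nothing in the documents supports an excess of that size or a full return.

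The primary feasibility endpoint is untouched. What suffers is the conclusion on perceived stress and the effect size handed to the larger trial.

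**What to change.** In Section 13:

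1. Remove the waitlist comparison, or reconcile it with the one-cohort design in Sections 6 and 8.
2. State the analysis as the within-person change from baseline to 7–10 weeks, with a 95% confidence interval.
3. Replace the conclusion that "our hypothesis that the program results in reduction of perceived stress will be supported" with a statement that perceived stress fell from before to after the program.
4. State that the effect size carried to the larger trial is an uncontrolled pre-post change and includes any drift.

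Sections 23 and 24 can add that consent comes first and that baseline follows the timing in Section 8.

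A Perceived Stress Scale score at consent is optional and descriptive only. The scale asks about the past 30 days, so scores taken less than a month apart would overlap, and lead-in lengths would differ between nurses. It also could not detect a workload change that coincides with training.

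The required changes are to text and reporting, with no added data, visits or staff. The price is a more modest conclusion on a secondary outcome.

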Medical Outcomes Study Questionnaire Short Form 36 (Ware and Sherbourne, 1992): The SF-36 is a 36-item self-report instrument for measuring health related quality of life. It contains 8 subscales: vitality, physical functioning, bodily pain, general health perceptions, physical role functioning, emotional role functioning, social role functioning, and mental health. It is perhaps the most widely used quality of life instrument in individuals without a specific medical disorder.

Self-Efficacy Scale (Marksherer, et al., 1982): The Self Efficacy Scale is a 30-item self-report instrument that asks participants to rate their agreement with statements about their attitudes and feelings.

Philadelphia Mindfulness Scale (Cardaciotto, et al., 2008): This 20-item self-report instrument was developed to measure present-moment awareness and acceptance. The items ask participants to rate how often they have encountered certain experiences over the past week.

Distress Tolerance Scale (Simons and Gaher, 2005): The Distress Tolerance Scale is a 15-item self-report instrument that asks participants to rate their agreement with statements about their beliefs about feeling distressed. It, along with the Philadelphia Mindfulness Scale, is being used to assess the core skills of DBT.

Cognitive Failures Questionnaire (Broadbent, Cooper, Fitzgerald & Parkes, 1982): This is a 25-item instrument that assesses the frequency of minor cognitive mistakes.

Mind Wandering Questionnaire (Mrazek, et al., 2013): This is a 5-item questionnaire assessing attention and mind wandering during daily life.

Resistance to Sunk Cost (Bruine de Bruin, Parker, & Fischhoff, 2007): This is 10-item scale that measures the tendency to continue a task once time, money, or effort has already been invested. This is a subscale of the Adult Decision-Making Competence scale.

At post (7-10 weeks) and 24 weeks, participants will be asked to complete:

Questionnaire on using skills in practice (if completed at least 75% of the educational program).

9) Study Timelines*

The following table depicts the assessments, measures and time points for the proposed data collection.

	Baseline	7-10 weeks	24 weeks
Demographics	X		
Perceived Stress Scale	X	X	
Maslach Burn Out Inventory	X	X	
Medical Outcomes Study Questionnaire Short Form 36	X	X	
Self-Efficacy Scale	X	X	
Philadelphia Mindfulness Scale	X	X	
Distress Tolerance Scale	X	X	
Cognitive Failures Questionnaire	X	X	
Mind Wandering Questionnaire	X	X	

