Resistance to Sunk Cost	X	X	
Questionnaire on using skills in practice		X	X

The participants are anticipated to complete the study between 6-7 months.

10) Study Endpoints*

The primary outcome will be feasibility defined by at least 75% of the participants completing at least 75% of the program. The secondary outcome will be changes in Perceived Stress Scale from baseline to post-intervention. Other secondary outcomes will be tested on a preliminary basis: changes in target skill areas (e.g., coping self-efficacy, mindfulness, and distress tolerance), burn out, and health-related quality of life from baseline to post-intervention.

11) Data Storage*

We are collecting data on participant demographics (e.g., age, sex, race/ethnicity, work location, nursing experience) and the following instruments/questionnaires: Perceived Stress Scale, Maslach Burn Out Inventory, SF-36, Self-Efficacy Scale, Philadelphia Mindfulness Scale, Distress Tolerance Scale, Cognitive Failures Questionnaire, Mind Wandering Questionnaire, Resistance to Sunk Cost and Questionnaire on using skills in practice.

All participant information will remain confidential and stored on the study PI's and research coordinators computers and in REDCap. Identifiers such as name will only be used during the initial data retrieval process and can be destroyed once all data records have been obtained and data analysis completed. REDCap is a free, secure, HIPAA-compliant web-based application hosted by the University of Miami's Research Information Technology. The REDCap system offers easy data management with audit

trails, reports for monitoring and querying participant records, and an automated export mechanism to statistical packages (SPSS, SAS, Stata, R/S-Plus). The program will include 8 sessions and each session will be recorded. The recordings will be done with a digital video camera. Files will be immediately downloaded after each session and will be uploaded privately to [name] Youtube Account. The videos will be accessible only to the participants with whom we share a link with and are not searchable online. The files will be also backed up to a secured server to which only lab members have access. These files will also be backed up on to an external hard drive and stored in a locked cabinet. After the files are backed up, they will be permanently deleted from the camera memory cards.

12) Data Management*

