To protect the confidentiality of participants, all data will be collected using study ID numbers and assessments will be completed on-line with an e-mail link to the questionnaires in RedCap. All participants will be assigned unique alphanumeric numbers as they enroll in the study. No personally identifying information will appear on any questionnaires or other material. All participant information will be de-identified at the Sylvester location or the University of Miami Coral Psychology Department in Coral Gables, Florida. Likewise, information matching the participant number to a name or other identifying information will be kept in a locked cabinet at the Sylvester location or UM Psychology Department. Only the study PI and research coordinator will have access to the key that links code names to real names.

Standard operating procedures specifying the rules, methods, and procedures to follow will be used and checked by the study staff.

The research coordinator will be in weekly contact with [name] to review any issues with the data (i.e., missing data) and ensure data integrity. A study team member will also review all consent forms to ensure that they are complete.

Velos database system will be used to help input participant demographics and study related information.

13) Data Analysis Plan*

Descriptive statistics will be compiled on the characteristics of the sample using data from the demographics questionnaire.

1. To determine the feasibility of a compassion training program for oncology nurses.
Hypothesis 1:
 - Demonstration of feasibility will be assessed by the number of individuals who drop out of the study prior to completing the post-intervention assessment and the rate of missed sessions. If drop-out rate or missed-session rate exceeds 25%, revisions to the intervention may be needed.
2. To explore changes in burn out, perceived stress, and coping skills after the training program.
Hypothesis 2:

- Investigate the effect of an educational program on perceived stress in nurses.
- Explore the effect of an educational program on three target skill areas (coping self-efficacy, mindfulness, and distress tolerance), burn out, and health related quality of life.

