All participant data will be kept in electronic files that are password protected and changed whenever staff changes. Only study staff will have access to the data. A link between ID number and participant's name will be kept in a separate file, also password protected (with a different password), accessible only to the study PI and research coordinator. The PI will work with the research coordinator to ensure that the data were accurately entered into the data storage system. For every new consent form, the PI (or designee) will review the form within one week of completion, and make an action plan to address any concerns that may arise. The research coordinator will present a quality control report to the PI on a bi-weekly basis.

Quality Plan for Monitoring Recruitment and Retention

The research coordinator will produce a weekly recruitment and retention report during the recruitment phase to be reviewed with the PI or designee. This report will yield important data in the event that changes to recruitment or retention procedures are required.

Protocol Integrity

Each individual educational session will be presented to the PI on a weekly basis, with a primary emphasis on what occurred during study sessions. The research coordinator will track the assessments to ensure that they are occurring at the appropriate times.

15) Withdrawal of Participants*

Participants will be informed that they have the right to discontinue participation at any time.

Participants may be withdrawn from the training at any time at the principal investigator's discretion due to:

- Non-compliance
- Clinical judgment of the investigator
- Worsening of clinical condition as reflected by 1) cognitive inability to complete assessments on 2 consecutive occasions 2) clear decline in psychosocial or behavioral functioning 3) safety concerns (aggression towards self or others) that, per clinician judgment, requires in-patient psychiatric care; 4) onset of new, severe psychiatric illness such as mania, psychosis, or severe depression.

If a participant decides to withdraw from the research, they will be thanked for their time and efforts. They will also be informed that their decision to withdraw from the study will in no way affect the medical treatment they receive at the University of Miami. Any data collected prior to withdrawal will be destroyed in compliance with IRB procedures.

Adverse events:

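### Section 15 destroys data collected before a voluntary withdrawal and exempts no enrolment, attendance or completion record, so two feasibility measures may lose the leavers' records

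*Combined protocol and SAP*

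**What the plan says.** The rule is in Section 15 (Withdrawal of Participants), in the paragraph that opens "If a participant decides to withdraw from the research". It reads: "Any data collected prior to withdrawal will be destroyed in compliance with IRB procedures". The paragraph has no exception, and the IRB procedures it refers to are not in the documents. An earlier paragraph of the same section deals with withdrawal by the investigator ("Participants may be withdrawn from the training at any time") and has no data rule of its own.

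Feasibility is defined in two places.
- Section 13, Hypothesis 1 (repeated from Section 3) uses "the number of individuals who drop out of the study prior to completing the post-intervention assessment and the rate of missed sessions", and adds: "If drop-out rate or missed-session rate exceeds 25%, revisions to the intervention may be needed".
- Section 10 makes the primary outcome "feasibility defined by at least 75% of the participants completing at least 75% of the program".

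No section names the attendance record that feeds these measures. Section 11 begins its list with "We are collecting data on participant demographics" and goes on to named questionnaires; attendance is not on it. Section 14 describes data collection as assessments. Attendance may be held elsewhere: Section 8 awards one education credit per hour attended, Section 11 has every session recorded and backed up, Section 12 mentions the Velos database, and Section 14 has sessions presented weekly to the principal investigator. None of these is said to survive a withdrawal or to supply the endpoint.

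**The concern.** Feasibility is the study's first objective, and the people who leave carry much of the evidence on it. A rule that erases what was collected from them, with no exception, acts selectively on that group and cannot be undone. If attendance falls under the rule, the study would know that a nurse left but not how many sessions she had attended. The missed-session rate needs that number. So does the primary outcome, for a nurse who had already attended three quarters of the sessions before withdrawing.

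The drop-out rate is safer. It needs only the number enrolled and whether each nurse completed the post assessment. The tracking forms in Section 14 and the gift card in Section 8 bear on completion, although Section 15 does not expressly protect that status either.

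**Working it through.** **Inputs.** At most 25 participants (Sections 6 and 22); 8 sessions (Section 8); trigger strictly above 25% (Section 13); 75% of participants and 75% of the program (Section 10). The 25% is a chosen threshold, so there is no calculation to reproduce. As a consistency check, 8 sessions × 2 hours = 16 hours, which matches the 16 credits.

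**Assumptions the plan does not state.** Attendance is destroyed; all 25 enrolled are the denominator; sessions after withdrawal count as missed; program completion is measured in sessions, so 75% of 8 = 6.

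**Thresholds.** 25 × 8 = 200 person-sessions, and 25% of 200 = 50, so 51 or more missed exceeds the trigger. For drop-out, 6/25 = 24% does not exceed 25% and 7/25 = 28% does.

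**Missed-session window.** Let w nurses withdraw, each having attended 1 to 4 sessions and so missed 7 to 4. Let M be the total missed by stayers. The verdict is open when M + 4w ≤ 50 and M + 7w ≥ 51, that is, 51 − 7w ≤ M ≤ 50 − 4w.

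| Withdrawals | Stayers | Open when stayers missed, in total | Per stayer |
|---|---|---|---|
| 1 | 24 | 44–46 | 1.8–1.9 |
| 2 | 23 | 37–42 | 1.6–1.8 |
| 3 | 22 | 30–38 | 1.4–1.7 |
| 4 | 21 | 23–34 | 1.1–1.6 |
| 5 | 20 | 16–30 | 0.8–1.5 |
| 6 | 19 | 9–26 | 0.5–1.4 |

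The window holds 3w values: 18 at six withdrawals, 3 at one.

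**Illustration.** Nineteen stayers miss one session each and six nurses withdraw.
- All six attend until they leave after session 2: (19 + 6 × 6)/200 = 55/200 = 27.5%, triggered.
- The same, leaving after session 3: (19 + 6 × 5)/200 = 49/200 = 24.5%, not triggered.
- Only a head count survives: between 19/200 = 9.5% and (19 + 48)/200 = 67/200 = 33.5%.

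**If withdrawal dates survive.** A nurse who leaves after session j has missed at least 8 − j. In the session-2 case at least 19 + 36 = 55 are missed, so the verdict is settled. In the session-3 case the total lies between 49 and 67 and stays open. For six leavers who each attended at least one session, the window becomes 9 ≤ M ≤ 50 − 6(8 − j): empty at j = 1, 9–14 at j = 2, 9–20 at j = 3 and 9–26 at j = 4. Dates therefore help most when exits are early.

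**If sessions after withdrawal are not counted.** With the session-2 leavers' records kept, the rate is 19/(152 + 12) = 19/164 = 11.6%. With them destroyed it is 19/152 = 12.5%. The verdict does not change.

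**Primary outcome.** 75% of 25 = 18.75, so 19 completers are needed. With 6 withdrawals and all 19 stayers completing, 19/25 = 76% and the outcome is met whatever was lost. If one stayer does not complete, it is 18/25 = 72%, or 19/25 = 76% if one leaver had already attended 6 sessions. With 7 withdrawals and all 18 stayers completing, the same two values arise.

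**The case against.** The strongest reply is that the open verdict depends on conditions that the plan does not impose. Attendance must count as data, no other record may survive, all enrolled nurses must be the denominator, and sessions after withdrawal must count as missed. Sections 11 and 14 describe the data as demographics and assessments, which points away from attendance. Credits cannot be awarded without knowing who attended. The unseen IRB procedures and consent pages may limit what is destroyed. A withdrawal date arises at withdrawal, so the rule does not plainly reach it, although no section says that one is recorded. And exceeding 25% means only that revisions may follow.

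All of this stands, and it limits the point. It does not remove it: the sentence covers any data, and no section says that attendance is kept or which record is the source.

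Three stronger readings are tempting, and the documents do not support them.
- A reader might infer that the skills questionnaire is also affected, because it is given only "if completed at least 75% of the educational program". A nurse who has left the research would not be sent it, so destroying her record changes nothing there.
- A reader might infer that the problem is confined to 1 to 6 withdrawals. That limit belongs to the drop-out trigger and to exits before the post assessment. Follow-up runs to 24 weeks, so a nurse can finish the post assessment, not be a drop-out, and still lose her data by withdrawing later. At 7 withdrawals the primary outcome can still be open.
- A reader might infer that the rule covers everyone who stops. It sits with voluntary withdrawal from the research. Nurses who merely stop attending are not clearly covered, and its application to those the investigator withdraws from the training is not stated.

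**Conclusion.** The point holds as a minor one. Read literally, Section 15 takes leavers' records out of the missed-session rate and the primary outcome. Under the stated assumptions this can decide the missed-session verdict over a sizeable window at 6 withdrawals and a very small one at 1. For the primary outcome it matters only near the 19-of-25 margin, and only if a nurse attended at least 6 sessions before withdrawing.

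A reader might go further and infer that the plan orders attendance destroyed and so cannot judge feasibility. The documents do not show that: the status of attendance is ambiguous, parallel records may exist, and the size of the effect depends on a denominator and counting rule that the plan leaves open. The calculations also use the maximum enrolment of 25; a smaller cohort would shift the figures.

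**What to change.** In Section 15, add after the destruction sentence:

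> This does not apply to the de-identified record of enrolment, sessions attended, withdrawal date and post-assessment completion, which is kept and used for the feasibility measures as far as the IRB and the consent allow.

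In Sections 10 and 13, state that the feasibility denominator is all enrolled participants and that sessions after withdrawal count as missed. Name the record that is the source for attendance.

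Two related clarifications are separate from this point: whether a session made up from a recording counts as missed, and whether the data rule applies to withdrawal by the investigator.

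The cost is an IRB amendment to Sections 10, 13 and 15 with consent wording aligned. Whether re-consent would be needed cannot be judged without the consent pages and the IRB procedures. Little or no data collection is added if attendance is already logged for credits. Counting all enrolled nurses and treating later sessions as missed may make the feasibility figures less favourable.
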